#### **Statistical analysis:**

Patients' percent change of Vitamin D (25 (OH)2D) was calculated to quantify the change levels before and after vitamin D3 (Cholecalciferol) administration through the equation:

Pediatric, Blood Vitamin D level (BVD) %change =

$$[(\text{BVD after} - \text{BVD before}) \div \text{BVD before}] \times 100$$

Collected data were entered and analyzed using the Statistical Package for Social Science Software (SPSS) program, version 21.0 IBM. Tests of normality of data (like Shapero-Wilk test) revealed that data isn't normally distributed. That's why non-parametric tests like MannWhitney and Kruskal-Wallis tests were used in univariable comparisons to quantify the associations of continuous variables. Data were summarized using the median and interquartile range for quantitative variables. Spearman correlation test was used to detect the relationship between continuous variables. P values below 0.05 were considered statistically significant. A multivariate Cox regression analysis model was conducted to explore the independent effect of vitamin D3 supplementation on the overall survival of pneumonic children.

Given the short period of the study follow-up and single intervention, there was no stopping rule or interim analyses.

All children randomized were included in the analysis on an intention-to-treat basis unless the outcome measures were missing (n = 0) or reported to have recovered or lost within 24 h (n = 0). Meantime to recovery for the episode of pneumonia at recruitment was compared for the vitamin D group and control group. Kaplan-Meier plots and log-rank tests were used to compare the time to recover from the index episode of pneumonia between the vitamin D and placebo groups.

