#### **Sample Size and study population**

To detect a 20% difference in the mean duration of pneumonia between the vitamin D arm and control arm [5 days vs. 6 days (SD 2)] allowing Type I error of 5% and Type II error of 10%, 86 per group (172 total) is the minimum number to be recruited [13]. After allowing for 10% for nonresponse or loss for follow-up and 25% for exclusion of children diagnosed with sufficient or toxic level of vitamin D after vitamin D testing (Box 1) according to prevalence of vitamin deficiency in a pediatric hospital of eastern India [14], 233 was the minimum number to start with. Mild and moderate pneumonia cases were recruited from two of the hospital general pediatric departments chosen by simple random sample from a total of six hospital departments while severe pneumonia cases were recruited from the four PICUs of the hospital.

All children (259 children) between 1 month and 12 years of age admitted to the selected departments during the period from 9th September 2019 to 15th December 2019 and diagnosed clinically with pneumonia according to World Health Organization criteria of severity [15] (Box 2) were screened for the inclusion criteria. Children who had clinical signs of rickets (2 children), severe illnesses (meningitis, heart or renal disorders, measles, severe malnutrition, endocrine dysfunction, hypercalcemia, hyperthyroidism, and suspected tuberculosis) (4 children) or were known to have received high-dose vitamin D treatment in the past 3 months (3 children) were excluded from the study. Children with sufficient (52 children) or toxic (7 children) levels of vitamin D were also excluded.

Thus, 191 child (93 in the intervention arm and 98 in the control arm) who had pneumonia with insufficient or deficient level of vitamin D and their parents consented to participate were actually enrolled in the study, completed the baseline and the outcome assessments and continued the daily clinical follow up till their discharge (improvement or death) from the hospital.

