**Box 1: Level of vitamin D [16]**

Sufficient vitamin D (25(OH)D:  $\geq 30$  ng/mL),

Insufficient vitamin D (25(OH)D or at risk of deficiency : 10-29 ng/mL), and

Deficient vitamin D (25(OH)D:  $<10$  ng/ mL).

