### **Outcomes assessment**

Outcomes were assessed 7 days after vitamin D injection, the first day whereas vitamin D reaches its maximum level in the blood [19] to guarantee the assessment of all participants before their

discharge. The primary outcome variables were changed in serum level of 25(OH)D, PaO2/FIO2, serum creatinine, C reactive protein, and serum bilirubin levels and platelets count. Also, the SOFA score for severe cases. The secondary outcomes included the fate of the cases (improvement or death) and the duration between enrolment and hospital discharge for improved cases.

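### Entry rests on absolute 25(OH)D cut-offs, but the only 25(OH)D response measure the plan defines is percent change, which does not show whether the deficit was corrected

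*Combined protocol and SAP*

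**What the plan says.** Eligibility is absolute. Under Sample Size and study population, "Children with sufficient (52 children) or toxic (7 children) levels of vitamin D were also excluded", which left 191 children "who had pneumonia with insufficient or deficient level of vitamin D". Box 1 gives the classes in ng/mL: sufficient at 30 or above, insufficient ("at risk of deficiency : 10-29 ng/mL") and deficient below 10.

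Under Outcomes assessment, "The primary outcome variables were changed in serum level of 25(OH)D", followed by the other laboratory measures. The text does not say whether the change is absolute or relative. On timing, "Outcomes were assessed 7 days after vitamin D injection".

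The Statistical analysis section supplies a scale: percent change, with the analyte written as 25 (OH)2D, "was calculated to quantify the change levels before and after vitamin D3 (Cholecalciferol) administration through the equation" [(after − before) ÷ before] × 100. The remaining methods are general: median and interquartile range, Mann-Whitney and Kruskal-Wallis tests, and Spearman correlation. No section plans a comparison of day-7 levels adjusted for baseline, or a count of children in each Box 1 class on day 7.

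**The concern.** The trial selects children for a deficit defined in ng/mL, on the premise that supplementation will help them. It then defines the response on a scale that carries no information about that deficit unless the baseline is known. Dividing by a low baseline inflates the score of the children who start furthest from the cut-off, so a larger score can go with less correction.

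A rise in 25(OH)D is expected in the treated arm simply because vitamin D was injected. A significant percent change would therefore show delivery. A reader could easily take it as evidence that the deficit was removed, and would then read the results for duration and fate in that light. How far the injection moved children out of the entry classes is the more useful fact, and the plan does not ask for it.

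A smaller point is the analyte name. The percent-change sentence writes 25 (OH)2D, while the assay, Box 1 and the outcome list all use 25(OH)D. The Introduction treats 1,25(OH)2D as a different marker with a different half-life, so the slip could mislead.

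**Working it through.** **The plan's own figures.** The flow reproduces: 259 − 2 − 4 − 3 = 250; 250 − 52 − 7 = 191 = 93 + 98. So 59 of 250 children (23.6%) were removed on vitamin D level alone. The sample size of 86 per group also reproduces (two-sample t-test, difference 1 day, SD 2, two-sided 5%, 90% power: 85.03, rounded up). It concerns duration of pneumonia and does not bear on the 25(OH)D measure.

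**Inputs from the documents.** The cut-offs of 10 and 30 ng/mL (Box 1) and the percent-change formula (Statistical analysis).

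**Inputs assumed.** The documents give no baseline distribution, expected rise or assay precision. The baselines, rises and errors below are illustrations.

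*Step 1: score against correction.* Percent needed to reach 30 = (30 − b) ÷ b × 100. Score for a rise g = g ÷ b × 100.

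| Baseline b | Needed to reach 30 | Rise of 10: score (end level) | Rise of 15: score (end level) |
|---|---|---|---|
| 5 | +500% | +200% (15) | +300% (20) |
| 10 | +200% | +100% (20) | +150% (25) |
| 15 | +100% | +67% (25) | +100% (30) |
| 20 | +50% | +50% (30) | +75% (35) |
| 25 | +20% | +40% (35) | +60% (40) |

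In both rise columns the highest score belongs to the child who ends lowest. For any equal rise, baseline 5 scores five times baseline 25, since (g ÷ 5) ÷ (g ÷ 25) = 5. If rises are instead proportional to baseline, the scores agree but correction still differs: +100% takes 5 to 10 and 10 to 20 (both insufficient), but 15 to 30 (sufficient).

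*Step 2: group summaries.* Assume baselines spread evenly over a band and an equal rise for all.

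- Baselines 3 to 10, rise 10: median score 10 ÷ 6.5 = +154%; none reach 30, since the highest end level is 20. Rise 15: 15 ÷ 6.5 = +231%; none reach 30.
- Baselines 10 to 30, rise 10: median score 10 ÷ 20 = +50%; (30 − 20) ÷ 20 = 50% reach 30. Rise 15: +75%; (30 − 15) ÷ 20 = 75% reach 30.
- Baselines 3 to 30, rise 10: median score 10 ÷ 16.5 = +61%; (30 − 20) ÷ 27 = 37% reach 30. Rise 15: +91%; (30 − 15) ÷ 27 = 56% reach 30.

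*Step 3: noise at low baselines.* Assume an error of 1 ng/mL in the baseline and a rise of 10.

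- Baseline 5, day-7 level 15: +200% becomes (15 − 4) ÷ 4 = +275% or (15 − 6) ÷ 6 = +150%.
- Baseline 25, day-7 level 35: +40% becomes (35 − 24) ÷ 24 = +46% or (35 − 26) ÷ 26 = +35%.

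In general a small baseline error moves the score by about after ÷ before² per ng/mL: 15 ÷ 25 = 60 points at baseline 5, and 35 ÷ 625 = 5.6 points at 25. If the error grows in proportion to the level, the gap narrows. A 10% error gives about 60 × 0.5 = 30 points at 5 and 5.6 × 2.5 = 14 points at 25.

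**The case against.** Several things can fairly be said for the plan.

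- **The outcome is named as a change in serum level, and the general methods could cover raw levels.** This stands. A reader might infer that the response is measured only as percent change. The documents do not support that: they are silent on the scale in the outcome list and do not exclude levels. Percent change is, however, the only 25(OH)D response measure they define.
- **Both values exist.** The formula needs the before and after levels, and missing outcomes are given as n = 0. A reader might infer that the trial cannot tell whether the deficit was corrected. It can, for all 191 children. The gap is in the planned analysis, not in the design or the data.
- **The spread is between children, not between arms.** This also stands. Randomisation balances baselines in expectation, and medians and rank tests limit the pull of extreme percentages. The comparison loses precision and clarity but is not biased.
- **Box 1 defines entry classes; no section sets 30 ng/mL as a treatment target.** This is fair, and it is a reason to use the class counts as description rather than as a test of success.
- **A day-7 level comes late.** The sample size assumes mean durations of 5 and 6 days, so for many children the day-7 level may follow recovery. A reader might hope that day-7 attainment would separate an injection that failed to correct the deficit from correction that does not help. It cannot do so, because it does not show the level during the illness.

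**Conclusion.** The point holds as one about the choice of measure and its interpretation. The plan defines percent change as its 25(OH)D response, and that scale does not map to the absolute cut-offs on which children were selected. Under an assumed equal rise, a child starting at 5 ng/mL scores five times a child starting at 25 and still ends 20 ng/mL lower. Under the even-spread assumption over 3 to 30 ng/mL, median scores of +61% and +91% go with 63% and 44% of children still below 30. These sizes rest on assumed baselines and rises; the mismatch of scale rests only on the formula and Box 1.

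The documents give no ground for saying that the arm comparison is biased, or that many treated children in fact stayed below 30 ng/mL. The effect on the trial as a whole is limited: 25(OH)D is one of several primary variables, and the sample size rests on duration.

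**What to change.** In the Statistical analysis section:

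1. State that the main 25(OH)D analysis is the day-7 level in ng/mL, compared between arms with adjustment for baseline 25(OH)D, on a log or rank scale if the levels are skewed.
2. Add, as a descriptive check on how far the injection corrected the deficit, the number and percent per arm in each Box 1 class on day 7 (below 10, 10–29, and 30 or above).
3. Keep percent change as description only.
4. Correct 25 (OH)2D to 25(OH)D.
5. Label items 1 and 2 post hoc if the codes had already been revealed. The text describes completed enrolment and normality tests already run, and Random allocation of study groups says that the codes were opened at final data analysis.
6. Do not present day-7 class membership as evidence of repletion during the illness.

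The cost is wording and a short reanalysis: both levels are already measured and the cut-offs already stand in Box 1. The downside is that the share reaching 30 ng/mL may look less favourable than a percent rise.

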**Random allocation of study groups**

The children were individually randomized into intervention or control groups using a random number sequence elicited in an Excel spreadsheet with no limitations. The allocation was further hidden by using closed dark envelopes. A biostatistician and an office secretary who were not members of the investigating team did independently the randomization, repackaging, sequencing, and allocation concealment. None of the study staff and participants' parents was aware of the drug or placebo being dispensed. The codes were revealed only at the time of final data analysis.

The children were followed clinically on a daily base by the three study pediatricians to assess the resolution or deterioration of signs and symptoms of pneumonia till being discharged from the hospital whether due to recovery or death. The routine treatment of inpatient children is free of charge in Abou ElReesh Children's hospital, while vitamin D was paid by the researchers to be given free of charge to the children in the intervention arm during the study period.

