### **Hospital follow-up**

Children were monitored with recording data every eight hours for respiratory rate, chest indrawing, oxygen saturation, auscultation findings, fever, feeding, cyanosis, and mental status. The child was discharged when fever and fast breathing were absent for 2 consecutive days.

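### The Cox model labelled overall survival can use only in-hospital deaths and ties the hazard ratio to length of stay; a direct comparison of the proportion who died should be the main mortality result

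*Combined protocol and SAP*

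**What the plan says.** All of this is in the combined protocol and SAP.

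- **Model (Statistical analysis).** "A multivariate Cox regression analysis model was conducted to explore the independent effect of vitamin D3 supplementation on the overall survival of pneumonic children". No time origin, horizon, censoring rule or covariate list is given.
- **End of observation.** Under Sample Size and study population, the 191 enrolled children (93 vitamin D, 98 control) "continued the daily clinical follow up till their discharge (improvement or death) from the hospital". Random allocation of study groups says the same: children were followed "till being discharged from the hospital whether due to recovery or death". No contact after discharge is described.
- **What triggers discharge (Hospital follow-up).** "The child was discharged when fever and fast breathing were absent for 2 consecutive days".
- **Outcomes (Outcomes assessment).** Whether the child improved or died is a secondary outcome. So is time from enrolment to discharge, but only in children who improved.
- **Other methods (Statistical analysis).** The univariable tests named are for continuous variables. Kaplan-Meier and log-rank are assigned to time to recovery, with no statement of how deaths enter. The analysis set is all randomised children, by intention to treat, with no missing outcomes.

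**The concern.** Overall survival means time to death whether or not the child is still in hospital. This trial cannot observe that, because vital status is known only up to discharge. The natural way to run the model is to censor survivors at discharge. Discharge, however, follows recovery, which is the process the treatment is meant to speed up. An arm that recovers faster loses person-time, so its death hazard can rise with no extra deaths. A reader told that the hazard ratio concerns overall survival would take it as a statement about the chance of dying.

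The quantity a clinician wants, the proportion who died in each arm, is fully observed, yet apart from this Cox model no method is named for comparing it.

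Two related gaps concern recovery. Duration in improved children conditions on an event after randomisation, so the groups compared are no longer the randomised ones if treatment affects survival. And death prevents recovery, so the meaning of the recovery curve depends on a rule that the plan does not state.

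**Working it through.** **1. The plan's own figures.** The sample size is set "To detect a 20% difference in the mean duration of pneumonia between the vitamin D arm and control arm": 5 vs 6 days, SD 2, alpha 5%, power 90%. The normal approximation gives 2 × (1.96 + 1.2816)² × 2² / 1² = 84.1, so 85 per arm; the t-based solution is 85.03, so 86. Then 172 × 1.35 = 232.2, so 233. Participant flow: 259 − 2 − 4 − 3 − 52 − 7 = 191. All reproduce. They concern duration of pneumonia; no number of deaths and no power for death is given.

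**2. Why length of stay enters the hazard ratio.** Under constant hazards, an arm's death rate is (proportion dying, m) / (mean days under observation, T). So

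HR = (m₁/T₁) / (m₀/T₀) = risk ratio × T₀/T₁.

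| Scenario | 5 vs 6 days | 7 vs 8 days |
|---|---|---|
| Equal risk of death (risk ratio 1) | HR = 6/5 = 1.20 | HR = 8/7 = 1.14 |
| Deaths halved (risk ratio 0.50) | HR = 0.50 × 1.20 = 0.60 | HR = 0.50 × 1.14 = 0.57 |
| Equal daily death hazard (HR 1) | risk ratio = 5/6 = 0.83 | risk ratio = 7/8 = 0.88 |

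The stays are assumptions. The 5 vs 6 in the plan is duration of pneumonia, not time in hospital.

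**3. Without constant hazards.** Simulation with a one-covariate Cox model, gamma-distributed stays (SD 2), survivors censored at discharge, and gamma death times with mean day 2, 5, 7 or 10 (coefficient of variation 0.5 or 1), the same in both arms; Monte Carlo error about 0.01 or slightly more.

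- Equal risk of death, 5-20% mortality: HR about 1.05-1.47 (5 vs 6) and 1.0-1.37 (7 vs 8). The low end is early death (mean day 2), when few children have yet been discharged.
- Deaths halved, 10% to 5%, mean death day 2/5/10: HR 0.52/0.69/0.88 (5 vs 6) and 0.49/0.58/0.81 (7 vs 8), against a risk ratio of 0.50.
- If discharged children are instead kept event-free to a common horizon (10% mortality, mean death day 5), the equal-risk HR is about 1.00-1.01. The missing censoring rule therefore decides the result.

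**4. Against sampling error.** 5% and 20% of 191 are about 10 and 38 deaths. SE(log HR) ≈ 2/√deaths = 0.63 and 0.32. The largest equal-risk shift in these scenarios relative to its SE is ln(1.316)/0.32 ≈ 0.86 SE, at 20% mortality.

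**5. Deaths in the recovery curve.** Constant hazards, control arm, mean time to exit 6 days, 10% mortality: the recovery hazard is 0.90/6 = 0.15 per day. Day-7 recovery with deaths censored is 1 − exp(−0.15 × 7) = 65.0%. With death as a competing event it is 0.90 × (1 − exp(−7/6)) = 62.0%. Across 5-20% mortality and both arms the gap is about 2 to 7 percentage points. If deaths stay in the risk set as never recovered, the gap is zero, because no losses are reported.

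**6. Improved-only duration.** Give both arms the same recovery hazard, 0.15 per day, with 10% deaths on vitamin D and 20% on control. The death hazards are 0.15 × 0.10/0.90 = 0.0167 and 0.15 × 0.20/0.80 = 0.0375. Mean duration in improved children is 1/0.1667 = 6.00 days against 1/0.1875 = 5.33. The arm with fewer deaths looks 0.67 day slower with no difference in recovery hazard.

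**The case against.** **The plan does compare deaths.** A reader might infer that it names no method at all for comparing deaths by arm. That goes too far: the Cox sentence is itself such a comparison. What stands is narrower: apart from that model, nothing is named for the proportion who died.

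**Intention to treat.** A reader might also infer that improved-only duration contradicts the intention-to-treat statement. The documents do not show this. Outcomes assessment defines an outcome; Statistical analysis defines the analysis set and separately compares time to recovery between arms. The two differ in scope and should be reconciled.

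**The recovery curves may be right.** If deaths were kept at risk, 1 minus Kaplan-Meier is the cumulative incidence of recovery. The gap is in specification; no error is proven.

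**The assumed times do not fit the documents.** This stands. "Outcomes were assessed 7 days after vitamin D injection", every enrolled child is said to have completed them, and no outcome is missing. Read literally, nobody died or left before day 7, whereas the assumed stays put many exits earlier. With all stays and deaths moved past day 7 (assumed mean stays from 9 vs 10 to 12 vs 13 days, mean death day 8-12), the equal-risk HR runs from about 1.01 to 1.67. The ranges above are therefore illustrations, not bounds.

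**Materiality.** The outcomes are secondary, the model is described as exploring an effect, and deaths may be few. This limits the weight of the point without removing it.

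**Conclusion.** The concern holds in this form. The model can use only in-hospital deaths. With survivors censored at discharge it estimates a cause-specific hazard that mixes risk of death with length of stay, so it should not be reported as overall survival. It would be wrong to say that the hazard ratio must exceed 1 whenever stays are shorter: it is near 1 if deaths come early, and in the illustrations it reaches about 1.47 otherwise. With deaths halved it can sit close to the risk ratio of 0.50 or look much weaker, up to about 0.9.

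The conclusion about what is estimated rests on the documents alone, given censoring at discharge; the sizes rest on assumed mortality, stays and death timing. The risk is misinterpretation more than false significance. The planned sample size is unaffected. This should be fixed, with medium confidence as to its practical size.

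**What to change.** 1. **Main mortality result.** Compare in-hospital death in all 191 children (93 vs 98): counts, risk difference and risk ratio with 95% CI. The cost is imprecision. The half-width 1.96 × √[p(1−p)(1/93 + 1/98)] is 6.2, 8.5 and 11.3 percentage points at 5, 10 and 20% mortality.
2. **Cox model.** Relabel it as the cause-specific hazard of in-hospital death and state its time origin, censoring rule and covariates, or drop it.
3. **Recovery.** Show the cumulative incidence of recovery in all randomised children with death as a competing event, state how deaths were handled, and label the log-rank as cause-specific if they were censored. Disclose the power cost of keeping deaths in the risk set: at 93 vs 98, 5 vs 6 days and equal mortality of 5/10/20%, log-rank power is about 0.59/0.44/0.25. With deaths censored it is 0.65-0.81, 0.52-0.77 and 0.31-0.72, depending on when deaths occur.
4. **Duration.** Keep improved-only duration as descriptive. An all-randomised Mann-Whitney with deaths ranked worst is optional, as a sensitivity analysis. It is a trade-off: at equal 20% mortality its power is about 0.6, against about 0.9 for improved children only.

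The trial is complete and, in the plan's words, "The codes were revealed only at the time of final data analysis". Any added comparison should therefore be labelled post hoc. No new data are needed.
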